Study Protocol

Official Title of the study: Effectiveness and safety of Chinese herbal medicine for hepatitis B virus-related acute-on-chronic liver failure: A multi-center, randomized and controlled trial

NCT number: not yet assigned

Date of the document: June 21, 2018

This prospective, multi-center, parallel, centrally randomized controlled trial was designed in accordance with the Consolidated Standards of Reporting Trials (CONSORT) and Standard Protocol Items: Recommendations for Interventional Trials (SPIRIT) guideline, which is led by the principal investigator from 302 military hospital in Beijing, will be carried out from September 2018 and December 2020 among 16 tertiary academic hospitals in China. Patients with hepatitis B virus (HBV) related Acute-on-chronic liver failure (ACLF) will be randomly allocated to the Chinese herbal medicine (CHM) group or the standard medical treatment (SMT) group in a 1:1 ratio. The last patient will be enrolled before August 2019 to make sure the availability of 48 week's survival status by the end of this study. We will decide whether to expand additional institutions to guarantee adequate enrolments after interim assessment of effective participant numbers around December 2018. Patients in the SMT group will receive the standard medical treatment, and patients in the CHM group will receive rhubarb decoction enema for 1 week and CHM for 8 weeks additionally. All patients will be followed at pre-designed time points after 8 weeks' observational period until August 30, 2020 for the primary outcome and secondary outcomes.

The study is consistent with Good Clinical Practice(GCP) guidelines and has been approved by 302 military hospital ethics review committee (2018007D). Written informed consent is requisite to be signed by the patients or the authorized person under the willingness. The privacy and data of all participants will be protected carefully before, during and after the trial.

Patients will be consented and enrolled by co-principal investigators at each institution and managed by care providers including residents, attending physicians and nurses according to the protocol. Most of the patients will be treated in hospital for 8 weeks so clinicians can supervise the administration of CHM, in addition, the policy of reimbursement filed by the lab results at determined time points will boost the regular follow-up of this study.

Diagnostic criteria

The diagnosis of HBV-ACLF refers to the guideline of liver failure issued by Chinese Group on the Study of Severe Hepatitis B (COSSH) in 2012. In this guideline, HBV-ACLF was described as acute decompensation of liver function within short time (28 days usually) in patients with previously diagnosed or undiagnosed chronic liver disease, reaching the following obligatory criteria: (1) asthenia combined with obvious symptoms of digestive tract, (2) quick progress of jaundice defined as total bilirubin (TBIL) greater than 10 mg/dl or increase 1mg/dl daily, (3) coagulopathy with prothrombin activity less than or equal to 40% or international normalized ratio (INR) greater or equal to 1.5 except other extrahepatic reasons and another dispensable item of decompensated ascites and/or hepatic encephalopathy. There are three grades classified by the degree of coagulopathy and liver complications.

The TCM syndrome was judged by two qualified senior TCM physicians simultaneously based on the published criteria to decide what CHM will be given, and the discrepancy will be solved by consulting another senior physician.

Inclusion criteria

(1) In-patients with ACLF. (2) Patients with chronic hepatitis B or compensated cirrhosis caused by HBV. (3) Patients who are willing to sign the informed consent. (4) Patients aged from 16 to 65 years old.

Exclusion criteria

(1) Acute liver failure, sub-acute liver failure, or chronic liver failure. (2) ACLF caused by another disease such as autoimmune disorder, drug, alcohol, toxin, parasites other than HBV. (3) Pregnant or lactating women. (4) Primary liver cancer. (5) Combined with other severe systemic diseases or mental disease. (6) Anti-HIV positive or combined with infection of hepatitis A, C, D, E virus or cytomegalovirus, Epstein-Barr virus. (7) Patients participating in other clinical trials three months back. (8) Patients unwilling to cooperate. (9) Poor compliance, unable to guarantee to complete the protocol. (10) Complicated by severe cerebral edema, severe infection, type I hepatorenal syndrome (HRS), and gastrointestinal hemorrhage. (11) Patients allergic to one of the Chinese herbs in this protocol.

Criteria for discontinuing or modifying allocated interventions

The study will end at once if severe adverse events associated with CHM occurs or sufficient evidence indicates that adding CHM is not superior to the SMT group. Besides, CHM will discontinue and the final status will be censored in the condition of liver transplantation or the onset of liver cancer. Allocated interventions can be changed upon participant's request. All these changes will be recorded and analyzed based on intention-to-treat (ITT).

Intervention

Standard medical treatment

The SMT include a high-calorie diet; nucleoside analogues for HBV DNA-positive patients; sodium restriction, diuretics and paracentesis combined with albumin infusion for ascites; lactulose and L-ornithine aspartate and lactulose for HE and hyper-ammonia; hemostatic treatment for gastrointestinal hemorrhage; antibiotics for infections and renal replacement for HRS and uremic symptoms. CHM formulas, whatever routes of administration, are prohibited in the SMT group.

Chinese herbal medicine formula

There are two kinds of CHM based on traditional Chinese Medicines (TCM) syndromes. The common components of the two CHM formulas include *Artemisiacapillaris* Thunb (30g), *Salvia miltiorrhiza* Bge (30g), *Rhizoma*

Atractylodis Macrocephalae (30g), Rubia cordifolia L (30g), Sieyesbeckiaorientalis L (30g). Additional four components of Paeoniae Radix Rubra (60g), Gardenia jasminoides Ellis (9g), Hedyotis diffusa Willd (30g), Bletilla striata (15g) are involved for excess syndrome, and five other components of Astragalus membranaceus (30g), Radix Pseudostellariae (15g), Radix Aconiti Lateralis Praeparata (10g), Galli Gigeriae Endothelium Corneum (20g), Polygonum cuspidatum Sieb.et Zucc (15g) are involved for deficiency syndrome. All ingredients are manufactured as a Chinese herbal granule in a specific weight ratio to the raw herb (Beijing Kang Rentang Pharmaceutical Co., Ltd, Beijing, China) in accordance with the quality criteria of Chinese pharmacopoeia in 2015. Patients will take one dosage of CHM granule per day for 8 weeks. For patients who cannot take oral medicine can be switched to colon route by the colonic therapy system (IMS-100A produced by Sunny Medical in Beijing China).

In addition, patients in the CHM group will also receive daily herbal enema of 100 microliter decoction composed by Radix et Rhizoma Rhei Palmati (Dahuang) 30g and Fructus Mume (Wumei) 30g for 7 days expect the following contraindications: (1) severe hemorrhoid, (2) female patients during menstruation, (3) anal stenosis, (4) artificial anal and (5) cardiac disease.

Outcome measurements

Primary outcome

The primary outcome is transplant-free survival at week 12.

Secondary outcomes

Secondary outcomes include (1) transplant-free survival at week 24, (2) the influence on liver function assessed by MELD score (involving levels of serum bilirubin, creatinine, INR and sodium) at week 12, (3) the influence on liver function assessed by Child-Pugh score (involving the serum bilirubin, coagulation function, albumin and the complication of hepatic encephalopathy and ascites) at week 12. (4) quality of life assessed by WHOQOL-BRIEF at week 12 and (5) the incidence of serious complications (including infections, encephalopathy, HRS, and gastrointestinal bleeding) from week 1 to week 24.

Safety outcomes

Primary vital signs, physical examinations, electrocardiogram and some laboratory tests such as routine blood test, urine test, renal function will be assessed before and after treatment to monitor the safety of this study. Furthermore, adverse events are also recorded in a predesigned case report form (CRF) through the whole study period. An independent safety committee will analyze the incidence and severity of adverse events to identify any unexpected adverse events or mortality in the CHM groups.

Other assessed parameters

Epidemiological characteristics, the details of nucleoside/nucleotide analog therapy, family history of liver disease were collected from patient medical record, the level of HBV DNA, endotoxin, and lymphocyte subsets were tested as well as CLIP-C-ACLF score were computed at week 24 and 48. The plasma level of HBV DNA, endotoxin, and cytokines were tested in ADICO clinical laboratories (Shanghai, China) which is blind to the allocation information. Remnant plasma will be stored at -80°C for ancillary studies. Women of childbearing age will undergo pregnancy test for the eligibility.

Sample size

The proposed -12% superiority margin of 8-week mortality rate was chosen based on our previous results of 30.87% in the SMT group. Considering a power of 0.80 and 10% of attrition rate, 255 subjects are needed for each group to achieve the significance level of 0.05 in assessing the difference between the two groups.

Randomization

The eligible patients will be randomly allocated to the SMT group and CHM group in a 1:1 ratio. The sealed numbers are generated by a computerized random number generator with statistical analysis system (SAS) software by an independent statistician from the center of clinical evaluation in China Academy of Chinese medical sciences (Beijing, China) and are concealed using opaque envelopes.

Trial monitoring

Trial monitoring is assumed by an independent Contract Research Organization so as to verify that: (1) The rights and well-being of human subjects are protected. (2) The reported trial data are accurate, complete, and verifiable from source documents. (3) The conduct of the trial is in compliance with the currently approved protocol/amendment(s), with GCP, and with the applicable regulatory requirement(s). Monitors should be appropriately trained and have the scientific and/or clinical knowledge needed to monitor the trial adequately. A risk-based monitoring strategy is developed in this trial, which includes on-site and centralized monitoring, which is more likely than routine visits to all clinical sites and 100% data verification to ensure subject protection and overall study quality. On-site monitoring is an in-person evaluation carried out by the monitor at the sites at which the clinical investigation is being conducted. Centralized monitoring is a remote evaluation carried out at a location other than the sites at which the clinical investigation is being conducted. Key monitoring processes include subject inclusion process; implementation of the inclusion criteria; source data verification; data integrity, etc.

Data management and Statistical methods

Data entry will be conducted by two independent administrators using online electronic CRF for accuracy and consistency. At the end of the study, the database will be locked and analyzed under the agreement of principal investigator and statistician, who are privileged to access the final trial dataset.

The randomized subjects who take at least one dose of CHM or SMT constitute the full analysis set (FAS) and those who complete all the visits constitute the per-protocol set (PPS). An efficacy assessment will be analyzed using FAS and PPS based on the principle of ITT. Subjects who have taken the CHM and been evaluated the safety at least once constitute the safety set (SS), which is used for safety evaluation. The statistical analysis will be performed using SAS 9.0 software (SAS Institute, Cary, NC, USA) by independent data management committee who are blind to the interventions.

Comparison of the two groups is conducted for the continuous variables with *t*-test and the categorical variables or rates with the chi-square test. The Kaplan-Meier overall survival curves will be generated and tested by log-rank. Cox proportional hazards regression model will be adopted to determine the prognostic factors associated with transplant-free survival. Multivariate logistic regression analyses will be adopted to explore factors associated with the incidence of liver-related complications. Subgroup analyses will be done based on the diagnostic criteria of Asian Pacific Association for the Study of the Liver (APASL) and European Association for the Study of the Liver (EASL) guideline.

The last observation carried forward approach was used for missing values. The statistical significance is defined as a two-sided $P < 0.05$.

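### The only written response to severe CHM-attributed events is to end the whole trial, and the safety set has no SMT comparator

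*Combined protocol and SAP*

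**What the plan says.** The section on criteria for discontinuing or modifying allocated interventions sets the safety stop in one clause: "The study will end at once if severe adverse events associated with CHM occurs". It adds nothing on how many events are needed or who takes the decision. A second trigger in the same sentence, lack of superiority, is outside this point.

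The same section has two provisions for individual patients. One covers transplantation and cancer: "CHM will discontinue and the final status will be censored in the condition of liver transplantation or the onset of liver cancer". The other covers patient choice: "Allocated interventions can be changed upon participant's request". Such changes are to be analysed by intention to treat.

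Under Safety outcomes, "adverse events are also recorded in a predesigned case report form (CRF) through the whole study period". The section continues: "An independent safety committee will analyze the incidence and severity of adverse events", and the stated purpose is "to identify any unexpected adverse events or mortality in the CHM groups".

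Under Data management and Statistical methods, the safety set is defined thus: "Subjects who have taken the CHM and been evaluated the safety at least once constitute the safety set (SS"). The full analysis set, defined just before it, admits patients who took either treatment.

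Under Sample size, "255 subjects are needed for each group", and the earlier 8-week mortality under SMT is given as 30.87%.

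**The concern.** A severe event judged to be related to CHM in a single patient has one written consequence, and it falls on the whole trial. There is no proportionate step in between: no CHM stop for that patient, no referral, no pause. The plan already has an independent safety committee, but the stopping clause does not mention it and the committee's description does not mention stopping.

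This matters because of the disease. With SMT mortality near 31% at 8 weeks, and infection, encephalopathy, hepatorenal syndrome and bleeding expected often enough to form a secondary outcome, severe events will be common in both arms. Whether one of them is due to the herbs or to liver failure is hard to judge in a single case. The usual safeguard is to look at the other arm, yet the safety set excludes SMT patients. If the clause is followed as written, the trial could end with transplant-free survival at week 12 unanswered, and without anyone having asked whether such events were more frequent than under SMT.

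**Working it through.** The plan gives no figure for the safety stop, so there is none to reproduce. The check has three parts.

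**1. Who decides, and on what.** The bodies named in the plan, set side by side:

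| Body | Section | Stated task | Stop decision assigned? |
|---|---|---|---|
| Independent safety committee | Safety outcomes | Analyse adverse events, looking for unexpected events or deaths under CHM | No |
| Contract research organisation | Trial monitoring | Verify participant protection, data and compliance | No |
| Data management committee | Data management and Statistical methods | Perform the statistical analysis | No |

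No section assigns the decision. The patient-level rules cover transplantation, liver cancer and patient request, but not a severe event attributed to CHM.

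**2. Background burden.** Inputs from Sample size: 255 per group (2 × 255 = 510 in all), 8-week SMT mortality 30.87%, and a 12% margin, taken here as an absolute reduction.

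- SMT arm: 255 × 0.3087 = 78.7, about 79 deaths by week 8.
- CHM arm if the hoped-for benefit is real: 255 × (0.3087 − 0.12) = 255 × 0.1887 = 48.1, about 48 deaths by week 8.

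So even a successful CHM arm would see dozens of deaths, before any non-fatal severe event is counted. Attributing one of them to CHM would meet the one-event reading of the clause.

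**3. Chance of a trigger, for illustration only.** Let p be the risk, per CHM patient, of a severe event attributed to CHM. The plan gives no p, so the values are assumed. Events are taken as independent across 255 patients.

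- One event suffices: 1 − (1 − p)^255.
- Two are needed (the plan uses the plural): 1 − (1 − p)^255 − 255p(1 − p)^254.

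| Assumed p | (1 − p)^255 | At least one | At least two |
|---|---|---|---|
| 0.02% | 0.950 | 5% | 0.1% |
| 0.1% | 0.775 | 23% | 3% |
| 0.5% | 0.279 | 72% | 36% |
| 1% | 0.077 | 92% | 72% |

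For example, at p = 0.5% the one-event figure is 1 − 0.279 = 0.721. The one-event chance reaches one half at p = 1 − 0.5^(1/255) = 0.0027, or about 0.27%.

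**The case against.** The strongest reply is that the rule errs on the side of patients, that an independent committee already reviews incidence and severity, and that nothing here biases the week-12 comparison if the trial runs to completion. That is fair. It limits the point to how the trial might end and how safety is compared; the primary analysis is not in question.

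Several stronger readings are tempting, and the documents do not support them.

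- **That no SMT safety data will exist.** Serious complications from week 1 to week 24, survival, and adverse events on the case report form are not restricted to CHM, and the general methods compare the two groups' rates by chi-square test. SMT data should therefore be available. What is missing is SMT patients in the safety set and a stated use of their data when a stop is considered. The CHM-only definition may be a slip of wording, but as written it governs the safety evaluation. Being an analysis population, it also does not determine what the committee may see during the trial.
- **That follow-up or analysis as randomised is lost when CHM stops in a patient.** The opening section follows all patients to August 30, 2020, and changes of treatment are analysed by intention to treat. This is largely covered.
- **That the 16 hospitals would apply the stop differently.** Ending the study is one trial-level decision. Sites might differ in how they attribute events, which is a narrower matter.
- **That severity and causality go ungraded in practice.** The case report form is not supplied and may carry those fields. The missing count and scales alone would be missing detail.
- **That the trial would probably be stopped.** The assumed risks span 50-fold, and the one-event results run from 5% to 92%. They show only that the outcome depends on a rate and a count that the plan does not give.

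**Conclusion.** The point holds in two parts. First, the only written response to severe events attributed to CHM is an immediate end to the whole study. On a literal reading one or two such events suffice, with no committee judgement, no comparison with SMT and no rule for the individual patient. Second, the safety set contains only patients who took CHM, so the planned safety evaluation has no comparator, even though the data for one should be collected.

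The size of the first part cannot be determined from the documents. It is small if attributed severe events are very rare (5% at an assumed 0.02%) and large if they are not (72% at 0.5%, 92% at 1%). These figures assume independent events, 255 patients exposed to CHM and a one-event trigger. The second part does not depend on any assumed rate. Both should be corrected; confidence is medium, because the count is ambiguous and the clause may not be applied literally.

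**What to change.** 1. In the discontinuation criteria, replace the automatic whole-study stop. When a severe event is attributed to CHM, CHM stops in that patient and the event goes promptly to the existing safety committee. The committee reviews adverse events in both arms and recommends continuing, pausing or stopping the trial. Follow-up and intention-to-treat analysis continue as the plan already provides.
2. Define the safety set as all randomised patients who received CHM or SMT and had at least one safety evaluation, and compare adverse events between arms.

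When the text is open, it would be sensible to name the severity and causality scales that the committee will use, if the case report form does not already carry them.

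The cost is an amendment to an ethics-approved protocol at 16 hospitals, with a wider committee remit. The committee and the case report form already exist. The downside is a short delay before any whole-study stop while the committee reviews; the affected patient is protected meanwhile because CHM has already stopped.

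### The plan censors patients at liver transplantation, although transplantation is a failure of the primary outcome, transplant-free survival at week 12

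*Combined protocol and SAP*

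**What the plan says.** - **Criteria for discontinuing or modifying allocated interventions:** "CHM will discontinue and the final status will be censored in the condition of liver transplantation or the onset of liver cancer". The same paragraph then says that changes to allocated interventions are recorded and analysed by intention to treat.
- **Primary outcome:** "The primary outcome is transplant-free survival at week 12".
- **Secondary outcomes:** "Secondary outcomes include (1) transplant-free survival at week 24".
- **Standard medical treatment:** "CHM formulas, whatever routes of administration, are prohibited in the SMT group".
- **Data management and Statistical methods:** three statements bear on the point. For time to event the plan states: "The Kaplan-Meier overall survival curves will be generated and tested by log-rank". The one regression that names the primary endpoint is described separately: "Cox proportional hazards regression model will be adopted to determine the prognostic factors associated with transplant-free survival". Group comparisons include "the categorical variables or rates with the chi-square test". Missing values are filled by last observation carried forward (LOCF).

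No section says that a transplant is an event, and none limits the censoring rule to a particular analysis.

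**The concern.** Transplant-free survival has two failure events, death and transplantation. The only explicit instruction on analysing a transplanted patient is to censor, which takes away the second event. An analyst who follows that instruction on the primary outcome is no longer estimating the outcome that the protocol names.

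Three further points are open.

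- **Which arm.** The sentence begins with CHM stopping, and the SMT group may not receive CHM. It can be read as covering CHM patients only or both arms.
- **How a censored patient enters a chi-square test.** The patient could be dropped from the denominator or, if the status is treated as missing, carried forward as alive.
- **Liver cancer.** The same sentence censors at onset of liver cancer, which is neither death nor transplantation. Stopping follow-up there sits badly with the intention-to-treat statement. The direction of this effect is not fixed, and it is not quantified here.

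If the choice stays open, it could be made after the transplant counts by arm are known.

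**Working it through.** The plan gives no transplant rate and no week-12 transplant-free survival rate, so it has no figure of its own to reproduce.

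**Inputs**
- SMT mortality 30.87% at 8 weeks and a planned difference of 12 points (Sample size section), so CHM 30.87 − 12 = 18.87%. Both are borrowed for week 12.
- Assumed cumulative transplant rates by week 12: 1%, 2%, 5% and 10%.

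**Formulas**, with d = pre-transplant death and t = transplantation, both cumulative to week 12:
- True transplant-free survival = 1 − d − t.
- Kaplan-Meier (KM) with transplants censored, constant hazards: total hazard H = −ln(1 − d − t); death hazard = H × d/(d + t); estimate = exp(−death hazard).
- Transplanted patients dropped from the chi-square: (1 − d − t)/(1 − t).

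**Base case, t = 5% in each arm**
- SMT: true 1 − 0.3087 − 0.05 = 64.13%. H = 0.4443; death hazard = 0.4443 × 0.3087/0.3587 = 0.3823; KM = 68.23% (+4.10 points). Dropped: 0.6413/0.95 = 67.51% (+3.38).
- CHM: true 1 − 0.1887 − 0.05 = 76.13%. H = 0.2727; death hazard = 0.2727 × 0.1887/0.2387 = 0.2156; KM = 80.61% (+4.48). Dropped: 0.7613/0.95 = 80.14% (+4.01).
- True difference: 76.13 − 64.13 = 12.00.
- Rule in both arms: 80.61 − 68.23 = 12.38 (KM); 80.14 − 67.51 = 12.63 (dropped).
- Rule in CHM only: 80.61 − 64.13 = 16.48 (KM); 80.14 − 64.13 = 16.01 (dropped).

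**Equal transplant use, true difference 12.0** (pairs are KM / dropped)

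| Transplanted | Overstatement per covered arm | Difference, rule in both arms | Difference, rule in CHM only |
|---|---|---|---|
| 1% | 0.7 to 0.9 | 12.1 / 12.1 | 12.9 / 12.8 |
| 2% | 1.4 to 1.8 | 12.1 / 12.2 | 13.8 / 13.6 |
| 5% | 3.4 to 4.5 | 12.4 / 12.6 | 16.5 / 16.0 |
| 10% | 6.6 to 8.9 | 12.8 / 13.3 | 20.9 / 19.9 |

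**Unequal transplant use (assumed), rule in both arms**

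| SMT | CHM | True difference | KM / dropped |
|---|---|---|---|
| 1% | 2% | 11.0 | 12.0 / 11.9 |
| 2% | 1% | 13.0 | 12.3 / 12.4 |
| 5% | 10% | 7.0 | 11.8 / 11.5 |
| 10% | 5% | 17.0 | 13.4 / 14.4 |

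**Sensitivity at 5% equal use**
- Mortality extended to 12 weeks at constant hazard, 1 − (1 − d)^1.5, gives 42.5% and 26.9%. True difference 15.6; both arms 16.1 / 16.4; CHM only 19.8 / 19.2.
- The plan does not say whether 30.87% includes deaths after transplantation. With pre-transplant death 5 points lower in each arm (25.87% and 13.87%), the overstatement is 3.6 to 4.6 points. True difference 12.0; both arms 12.4 / 12.6; CHM only 16.6 / 16.3.

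**Check with patient counts.** Take 255 per arm with transplants spread evenly over 84 days. With 79 deaths and 13 transplants, the true rate is (255 − 92)/255 = 63.9%. Censoring gives 68.1%, dropping gives 163/242 = 67.4%, and carrying forward as alive gives 176/255 = 69.0%. Two identical arms with the rule in CHM only would therefore show a false CHM advantage of 3.4 to 5.1 points.

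**The case against.** The best defence is that the rule was meant for overall survival. It speaks of a final status and does not name the week-12 outcome. The introduction refers to survival status at 48 weeks, and the Kaplan-Meier curves are labelled overall survival, where censoring at transplantation is an ordinary choice. Week-12 transplant-free survival would then be a simple rate for the chi-square test, with transplanted patients failing by the endpoint's name, and nothing would be biased. This reading is possible, but no sentence states that limit. The Cox model also treats transplant-free survival as time-to-event data, to which a censoring rule naturally applies.

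A second objection is that the large between-group figures need either the CHM-only reading or assumed imbalances. That stands as a description of size: with both arms covered and equal use, the difference shifts by at most 1.3 points even at 10% transplanted, and by 0.1 to 0.2 points at 1% to 2%. The clause on censoring carries no arm restriction of its own, so CHM-only is the worst case and not the established reading. But the rates in each arm are still overstated, and nothing in the plan ensures equal transplant use.

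Nor does intention to treat settle the matter. It fixes the arm in which a patient is analysed, not whether a transplant is an event.

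**Conclusion.** The concern holds, and the text must be corrected before analysis. A written rule conflicts with the definition of the primary endpoint. The harm is conditional on the rule being applied to that endpoint. Where it is, the week-12 rate is overstated in any covered arm with a transplant by week 12; the exception is the extreme case in which everyone else at risk dies. A transplant after week 12 leaves the week-12 estimate unchanged.

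The sizes rest on assumed transplant rates and, in the base case, on 8-week mortality standing in for week 12. They show that the effect can range from under 1 point to about 9 points per arm. They do not predict what this trial will see. The severity comes from this being the primary endpoint, not from the assumed sizes.

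**What to change.** Reconcile the discontinuation section, the outcome definitions and the statistical methods in one paragraph that states:

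1. In both arms, the event for transplant-free survival at weeks 12 and 24 is the first of death or liver transplantation.
2. A transplanted patient counts as a failure for this endpoint and is not censored, excluded or filled by LOCF.
3. This event is used for the week-12 comparison and for a Kaplan-Meier and log-rank analysis of transplant-free survival.
4. The overall-survival curves may stay as a separate supportive analysis, with their handling of transplants stated.
5. Under intention to treat, patients who develop liver cancer stay in follow-up for this endpoint and are not censored at its onset.

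No change to the rule on stopping treatment is proposed. The cost is the wording alone, because transplant dates are needed anyway for the stated primary outcome.

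### Censoring survival status at a new liver-cancer diagnosis drops later deaths and transplants that the transplant-free survival endpoint counts

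*Combined protocol and SAP*

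**What the plan says.** Under *Criteria for discontinuing or modifying allocated interventions*, the protocol states that "CHM will discontinue and the final status will be censored in the condition of liver transplantation or the onset of liver cancer". After a sentence allowing a change of intervention at the participant's request, the paragraph closes with "All these changes will be recorded and analyzed based on intention-to-treat (ITT").

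Under *Primary outcome*: "The primary outcome is transplant-free survival at week 12". The first secondary outcome is "transplant-free survival at week 24". Neither is restricted by cause of death, and neither names liver cancer as a component.

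Under *Data management and Statistical methods*: "An efficacy assessment will be analyzed using FAS and PPS based on the principle of ITT". The planned methods include "The Kaplan-Meier overall survival curves will be generated and tested by log-rank", comparison of "the categorical variables or rates with the chi-square test", and "The last observation carried forward approach was used for missing values". The section does not say which of these tests carries the primary outcome.

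The opening section has all patients followed to 30 August 2020 and sets the last enrolment date so that 48-week survival status is available. *Exclusion criteria* lists primary liver cancer, so the rule can only concern cancer diagnosed after entry.

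No section brings back deaths after a cancer diagnosis, specifies a competing-risk method, or plans a sensitivity analysis.

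**The concern.** Censoring is for patients whose outcome is no longer observed. A new liver-cancer diagnosis does not have that effect here: the patient remains in follow-up and vital status should be obtainable. Nor is the diagnosis itself a failure under the endpoint. A patient diagnosed at week 6 who dies at week 10 has failed transplant-free survival at week 12, yet under the rule that death is not counted.

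The censoring is also plausibly informative. Kaplan-Meier treats a censored patient as having the same future risk as those still followed, and patients with a newly found liver cancer may well not.

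The scope of the rule is unclear as well. The sentence begins with stopping CHM, which only one arm receives. It does not say whether SMT patients with liver cancer are censored. If they are not, SMT deaths after diagnosis would count and CHM deaths would not, and the comparison would be tilted towards CHM.

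**Working it through.** **1. The text.** The plan gives no figure that depends on this rule, so the main check is to follow one patient (cancer at week 6, death at week 10) through each provision.

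- *Endpoint definition:* failure by week 12.
- *Censoring rule with Kaplan-Meier and log-rank:* the patient leaves the risk set at week 6, so the death at week 10 falls after the censoring time and is not counted.
- *Censoring rule with a week-12 rate, chi-square and LOCF:* the last status before censoring is alive, so the patient would plausibly be carried forward as a survivor.
- *ITT for efficacy (statistical section):* the patient is followed to the endpoint whether or not treatment stopped, so the death counts.

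The censoring rule disagrees with both the endpoint and the ITT statement.

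**2. Inputs for size.** From *Sample size*: 255 per group; SMT mortality 30.87%; CHM mortality 30.87 − 12 = 18.87% if the 12% is absolute. These are 8-week rates, used here as a stand-in for week 12. Assumed, because the documents give neither: onset *c* of 1–3%, and risk of death after diagnosis *d* of 50%.

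**3. Censored patients counted as survivors.** Overstatement of an arm's survival = *c* × *d*.

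- Low: 0.01 × 0.50 = 0.5 points (255 × 0.005 = 1.3 deaths).
- High: 0.03 × 0.50 = 1.5 points (255 × 0.015 = 3.8 deaths).

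Each uncounted death is worth 1/255 = 0.39 points on this method.

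**4. Kaplan-Meier, onset near entry.** A censored patient is implicitly given the risk *m* of those who remain, so the overstatement is about *c* × (*d* − *m*).

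| Arm (*m*) | *c* = 1% | *c* = 3% |
|---|---|---|
| SMT (0.3087) | 0.01 × 0.1913 = 0.19 points | 0.03 × 0.1913 = 0.57 points |
| CHM (0.1887) | 0.01 × 0.3113 = 0.31 points | 0.03 × 0.3113 = 0.93 points |

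The range is therefore about 0.2–0.9 points. Later onset moves it towards step 3.

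**5. Sensitivity to the assumptions.** With *c* of 1–5% and *d* of 30–90%, step 3 gives 0.01 × 0.30 = 0.3 points up to 0.05 × 0.90 = 4.5 points (0.8 to 11.5 deaths per 255). Under step 4 with *d* = 30% in SMT, the bias is 0.05 × (0.30 − 0.3087) = −0.04 points. Its sign therefore rests on post-diagnosis risk exceeding that of the other patients.

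**6. Difference between arms.**

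- *Same rule and same onset in both arms:* counted as survivors, the term *c* × *d* cancels and the difference stays at 12.0 points. Under early Kaplan-Meier censoring, reading the planning rates as whole-arm mortality, it is 12/(1 − *c*): 12.1 at 1%, 12.4 at 3%, 12.6 at 5%.
- *CHM patients only censored:* the bias towards CHM is the CHM figure alone, 0.3–0.9 points (step 4) or 0.5–1.5 points (step 3).
- *Same rule, unequal onset (2% against 5%, d = 90%), counted as survivors:* 12 ± (0.05 − 0.02) × 90 = 12 ± 2.7, or 9.3 to 14.7 points.

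**The case against.** Several counter-arguments have force.

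- **ITT in the same paragraph.** A reader might infer that the paragraph contradicts itself, censoring in one sentence and invoking ITT two sentences later. The documents do not settle this: the ITT sentence directly follows the one on changing interventions at the participant's request and may cover only such changes. The firmer conflict is with the endpoint definition and with the ITT statement in the statistical section, and that conflict stands.
- **CHM-only censoring.** A reader might infer that the rule censors only the CHM arm. The clause on final status names no arm, and it also covers transplantation, which can occur in either. One-sided censoring is a possible reading that calls for clarification, not an established fact.
- **End of follow-up.** A reader might infer that follow-up stops at the diagnosis. The opening section says otherwise. The rule changes what is counted, not what is collected.
- **Worse prognosis.** The documents give no prognosis for new liver cancer, and the comparison group is liver-failure patients with about 31% mortality at 8 weeks on SMT. Informative censoring is plausible but not shown.
- **Practical weight.** Primary liver cancer is excluded at entry and the primary outcome is at week 12, so few patients are likely to be affected. Nothing in the documents suggests unequal onset, which the 9.3–14.7 range needs. The transplantation half of the sentence probably matters more.

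These points limit the size of the problem. None of them supplies a provision under which a death after the diagnosis would be counted.

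**Conclusion.** The concern holds as a mismatch between the censoring rule and the endpoint. Following the rule as written drops deaths and transplants that transplant-free survival counts at weeks 12 and 24, and this departs from the ITT principle set for efficacy.

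On assumed rates of 1–3% onset and 50% later death, an arm's survival is overstated by about 0.2–0.9 points with early Kaplan-Meier censoring, or about 0.5–1.5 points if censored patients are counted as survivors. The larger range should not be attached to Kaplan-Meier censoring near entry. The week-12 effect is probably small; it could be larger at week 24, with more time for both diagnosis and death.

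A reader might conclude that the treatment comparison is materially biased. The documents do not support that: with the same rule and the same onset in both arms, the 12-point design difference moves by 0.6 points at most even at 5% onset. A bias towards CHM arises if only CHM patients are censored, which the wording leaves open. The correction is worth making because it is cheap and removes that ambiguity.

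**What to change.** For the survival endpoints:

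1. Remove liver cancer from the censoring rule.
2. State that a death or transplant after a new liver-cancer diagnosis counts as an event on its own date, in both arms.
3. Keep censoring at liver cancer only as a sensitivity analysis, applied identically to both arms, with the date of onset defined.
4. Reconcile the transplantation half of the same sentence at the same time: transplantation is a failure under transplant-free survival, so censoring at it conflicts with the endpoint's own name. Correcting that half alone would leave the liver-cancer clause in place.
5. Separate the sentence on stopping CHM from the sentence on outcome status. When treatment stops is left to the sponsor.

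The cost is protocol and SAP wording. Follow-up of all patients and 48-week survival status are already planned, and adverse events are already recorded throughout the study. The sample size does not change.
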